6.5 Accrual Rate

6.5.1 Twenty in one year (approximately two per month)

6.6 Length of Study

6.6.1 The approximate length of the study will be one year.

7.0 Data Management

Informed consent document	EPIC
Protocol registration form (Appendix B)	WISER/OnCore
Baseline Data Collection (Appendix D)	WISER/OnCore
Surgery Form (Appendix E)	WISER/OnCore
Wound Form (Appendix F)	WISER/OnCore
30-Day Follow-up Form (Appendix G)	WISER/OnCore
Quality of Life (SF-36) (Appendix H)	WISER/OnCore
Adverse Events Log (Appendix I)	WISER/OnCore

8.0 Confidentiality and Privacy

Confidentiality will be protected by collecting only information needed to assess study outcomes, minimizing to the fullest extent possible the collection of any information that could directly identify subjects, and maintaining all study information in a secure manner. To help ensure subject privacy and confidentiality, only a unique study identifier will appear on the data collection form. Any collected patient identifying information corresponding to the unique study identifier will be maintained on a linkage file, stored separately from the data. The linkage file will be kept secure, with access limited to designated study personnel. Following data collection, subject identifying information will be destroyed six years after closure of the study, by deleting the linkage files consistent with data validation and study design, producing an anonymous analytical data set. Data access will be limited to study staff. Data and records will be kept locked and secured, with any computer data password protected. No reference to any individual participant will appear in reports, presentations, or publications that may arise from the study.

9.0 Data Safety and Monitoring

The principal investigator will be responsible for the overall monitoring of the data and safety of study participants. The principal investigator will be assisted by other members of the study staff.

10.0 Adverse Events List and Reporting Requirements

10.1 Adverse Event List for Tertiary Closure

10.1.1 Infection

As a result of enrollment onto this trial, there is a risk of developing a wound infection. This infection could be minor (skin redness). A wound infection could also involve the deeper tissues underneath the skin. If that occurs, the incision is typically re-opened and the deeper tissues are cleaned, irrigated and packed with a dressing. Rarely, a serious wound infection causes you to develop a fever or generalized infection. Treatment of a more serious wound infection could involve the following: re-admission to the hospital, intravenous antibiotics or additional surgery.

Enrolled patients will be at medium to high risk for wound complications in general. Wound complications usually occur within the first 30 days of surgery. Incisional hernia is a more "long-term" complication of a surgical wound. This complication can occur up to 1 year after surgery. Enrolled patients will be monitored carefully for wound complications using our standard care approach for patients with medium to high risk for wound complications.

10.2 Adverse Event Characteristics

- **CTCAE term (AE description) and grade:** The descriptions and grading scales found in the revised NCI Common Terminology Criteria for Adverse Events (CTCAE) version 4.0 will be utilized for AE reporting. All appropriate treatment areas should have access to a copy of the CTCAE version 4.0. A copy of the CTCAE version 4.0 can be downloaded from the CTEP web site (<http://ctep.cancer.gov>).
- **'Expectedness':** AEs can be 'Unexpected' or 'Expected' (see Section 7.1 above) for expedited reporting purposes only.
- **Attribution of the AE:**
 - Definite – The AE is **clearly related** to the study treatment.
 - Probable – The AE is **likely related** to the study treatment.
 - Possible – The AE **may be related** to the study treatment.
 - Unlikely – The AE is **doubtfully related** to the study treatment.
 - Unrelated – The AE is **clearly NOT related** to the study treatment.

10.3 STRC SAE Reporting Requirements

The Safety and Toxicity Reporting Committee (STRC) is responsible for reviewing SAEs for WFBCCC Institutional studies as outlined in [Appendix C](#). STRC currently requires that all unexpected 4 and all grade 5 SAEs on these trials be reported to them for review. All WFBCCC Clinical Protocol and Data Management (CPDM) staff members assisting a Principal Investigator in investigating, documenting and reporting an SAE qualifying for STRC reporting are responsible for informing a clinical member of the STRC as well as the entire committee via the email notification procedure of the occurrence of an SAE.

10.4 WFUHS IRB AE Reporting Requirements

Any unanticipated problems involving risks to subjects or others and adverse events shall be promptly reported to the IRB, according to institutional policy. Reporting to the IRB is required regardless of the funding source, study sponsor, or whether the event involves an investigational or marketed drug, biologic or device. Reportable events are not limited to physical injury, but include psychological, economic and social harm. Reportable events may arise as a result of drugs, biological agents, devices, procedures or other interventions, or as a result of questionnaires, surveys, observations or other interactions with research subjects.

All members of the research team are responsible for the appropriate reporting to the IRB and other applicable parties of unanticipated problems involving risk to subjects or others. The Principal Investigator, however, is ultimately responsible for ensuring the prompt reporting of unanticipated problems involving risk to subjects or others to the IRB. The Principal Investigator is also responsible for ensuring that all reported unanticipated risks to subjects and others which they receive are reviewed to determine whether the report represents a change in the risks and/or benefits to study participants, and whether any changes in the informed consent, protocol or other study-related documents are required.

Any unanticipated problems involving risks to subjects or others occurring at a site where the study has been approved by the WFUHS IRB (internal events) must be reported to the WFUHS IRB within 7 calendar days of the investigator or other members of the study team becoming aware of the event.

Any unanticipated problems involving risks to subjects or others occurring at another site conducting the same study that has been approved by the WFUHS IRB (external events) must be reported to the WFUHS IRB within 7 calendar days of the investigator or other members of the study team becoming aware of the event.

Any event, incident, experience, or outcome that alters the risk versus potential benefit of the research and as a result warrants a substantive change in the research protocol or informed consent process/document in order to insure the safety, rights or welfare of research subjects.

Appendix A – Subject Eligibility Checklist

IRB Protocol No. 00055298	Protocol No CCCWFU 04418					
Study Title: Secondary versus Tertiary Wound Closure in High Risk Gynecologic Abdominal Surgical Incisions						
Principal Investigator: [name].						
Inclusion Criteria (as outlined in study protocol)	Criteria is met	Criteria is NOT met	Source Used to Confirm * (Please document dates and lab results)			
Patients with high risk class II, class III, class IV abdominal wounds						
Undergoing laparotomy for gynecologic related disorders						
Patients undergoing laparotomy for both benign and malignant diagnoses will be included in this study						
Exclusion Criteria (as outlined in study protocol)	Criteria NOT present	Criteria is present	Source Used to Confirm * (Please document dates and lab results)			
Pregnancy						
Allergy to triclosan						
Patients undergoing HIPEC						

This subject is eligible / ineligible for participation in this study.

OnCore Assigned PID: _____

Signature of research professional confirming eligibility: _____

Date: _____ / _____ / _____

Signature of Treating Physician**: _____

Date: _____ / _____ / _____

* Examples of source documents include clinic note, pathology report, laboratory results, etc. When listing the source, specifically state which document in the medical record was used to assess eligibility. Also include the date on the document. Example: "Pathology report, 01/01/14" or "Clinic note, 01/01/14"

**Principal Investigator signature can be obtained following registration if needed

Appendix B – Protocol Registration Form

DEMOGRAPHICS

Patient: Last Name: _____ First Name: _____

MRN: _____ DOB (mm/dd/yy): ____ / ____ / ____

ZIPCODE: _____

SEX: Male Female

Ethnicity (choose one): Hispanic

Non-Hispanic

Race (choose all that WHITE BLACK ASIAN

apply): PACIFIC ISLANDER NATIVE AMERICAN

Height: _____.____ inches Weight: _____.____ lbs. (actual)

Surface Area: _____.____ m²

Primary Diagnosis: _____

Date of Diagnosis: ____ / ____ / ____

Performance Status: ____ ECOG

PROTOCOL INFORMATION

Date of Registration: _____ / _____ / _____

MD Name (last): _____

Informed written consent: YES NO

(consent must be signed prior to
registration)

Date Consent Signed: _____ / _____ / _____

PID # (to be assigned by OnCore): _____

Protocol Registrar can be contact by calling [contact] between 8:30 AM and 4:00 PM, Monday – Friday.

*Completed Eligibility Checklist and Protocol Registration Form must be hand delivered, faxed or e-mailed to
the registrar at [name] or [contact].*

Appendix C – Mandatory STRC SAE Reporting Guidelines

Safety and Toxicity Review Committee (STRC; previously known as CROC) Serious Adverse Event (SAE) Notification SOP	Date: 07/10/2019
---	-------------------------

Mandatory STRC SAE Reporting Requirements in WISER

This document describes reporting requirements of adverse events from **WFBCCC Investigator Initiated interventional trials to the Safety and Toxicity Review Committee (STRC)**. A trial is considered a **WFBCCC Investigator Initiated interventional trial** if the following criteria are met:

- 1) The Principal Investigator (PI) of the trial is a member of a department at the Wake Forest University Baptist Medical Center.
- 2) WFBCCC is considered as the primary contributor to the design, implementation and/or monitoring of the trial.
- 3) The trial is designated as “Interventional” using the Clinical Research Categories definitions provided by the NCI in the Data Table 4 documentation.
(<https://cancercenters.cancer.gov/GrantsFunding/DataGuide#dt4>)

There are two distinct types of WFBCCC Investigator Initiated interventional trials based on where patient enrollment occurs. These include:

- 1) Local WFBCCC Investigator Initiated interventional trials defined as trials where **all patients are enrolled from one of the WFBCCC sites**. These include the main outpatient Cancer Center clinics (located in Winston-Salem) as well as WFBCCC affiliate sites located in Bermuda Run (Davie Medical Center), Clemmons, Lexington, High Point, or Wilkesboro.
- 2) Multi-Center WFBCCC Investigator Initiated interventional trials defined as trials where patients are enrolled from other sites in addition to WFBCCC sites.

There are three types of trials that are included in this category:

- a. Trials sponsored by the NCI Community Oncology Research Program (NCORP) that are conducted at multiple sites where the PI is a member of a department at the Wake Forest University Baptist Medical Center.
- b. Trials sponsored by Industry that are conducted at multiple sites and the PI is a member of a department at the Wake Forest University Baptist Medical Center.
- c. Trials sponsored by WFBCCC that are conducted at multiple sites and the PI is a member of a department at the Wake Forest University Baptist Medical Center.

All Adverse Events (AEs) and Serious Adverse Events (SAEs) that occur on any patients enrolled on WFBCCC Investigator Initiated Interventional trials must be entered into the WISER system. The only exception to this requirement is for patients enrolled on NCORP trials at non- WFBCCC sites. AEs and SAEs for NCORP patients enrolled at WFBCCC sites must be entered into the WISER system. Once these AEs and SAEs are entered in WISER, certain actions must be taken regarding the reporting of specific Adverse Events to the STRC.

All Adverse Events that occur during protocol intervention (defined below) and are coded as either 1) **unexpected grade 4**, 2) **unplanned inpatient hospitalization > 24 hours (regardless of grade)**, or **grade 5 (death)** must be reported to the STRC using the SAE console in WISER.

A research nurse or clinical research coordinator when made aware that an adverse event meets one of the above criteria has occurred on a WFBCCC Investigator Initiated interventional trial, is responsible for informing a clinical member of the STRC by phone (or in-person) about the adverse event. The nurse/coordinator should contact the treating physician prior to calling the STRC clinical member to obtain all details of the SAE, as well as all associated toxicities to be recorded along with the SAE. In addition, this nurse or coordinator is responsible for entering the adverse event information into the SAE console in WISER. Once the adverse event has been entered into the SAE console an email informing the entire STRC committee will be generated.

THESE REPORTING REQUIREMENTS APPLY TO any staff member on the study team for a WFBCCC Institutional Interventional trial. Ultimately, the protocol PI has the primary responsibility for AE identification, documentation, grading and assignment of attribution to the investigational agent/intervention. However, when an AE event as described above is observed, it is the responsibility of the person who observed the event to be sure that it is reported to the STRC.

What is considered during protocol intervention?

During protocol intervention is considered to be the time period while a patient is on study treatment or during the time period within 30 days of last study treatment (even if patient begins a new (non-study) treatment during the 30 days). This window of 30 days should be the standard window to be used in all protocols unless a specific scientific rationale is presented to suggest that a shorter window can be used to identify events. If it is a trial sponsored by Industry and the sponsor requires a longer window for monitoring of SAEs, then the longer window of time specified by the sponsor should be followed.

What is considered as an Unexpected Grade 4 event?

Any grade 4 event that was not specifically listed as an expected adverse event in the protocol should be considered as unexpected. A grade 4 adverse event can be considered to be unexpected if it is an event that would not be expected based on the treatment being

received or if it is unexpected based on the health of the patient. In either case, if there is any uncertainty about whether a grade 4 adverse event is expected or unexpected it should be reported to STRC.

STRC notification responsibilities of the person (e.g., nurse) handling the reporting/documenting of the SAE in WISER:

1. Make a phone call (or speak in person) to the appropriate clinical member of the STRC as listed below (page if necessary)
2. Enter a new SAE into the SAE module that is located in the Subject>> CRA Console in WISER **WITHIN 24 HOURS** of first knowledge of the event. Information can be entered and saved, but the STRC members will not be notified until a date is entered into the STRC Notification Date Field. This will ensure that all persons that need to be made aware of the event (i.e., study team members and STRC members) will be notified; remember to file a copy of the confirmation.
3. Document that the appropriate person(s) on the STRC has been contacted. Indicate the name of the STRC clinician that was contacted in the Event Narrative field in the SAEconsole of the particular subject.
4. Document whether or not the protocol should be suspended based on the discussion with the STRC clinician. This is the major function of the email notification. Enter whether the protocol should be suspended in the Event Narrative Field.
5. Follow up/update the clinical member(s) of STRC regarding any new developments or information obtained during the course of the SAE investigation and reporting process.

Elements needed to complete the SAE form in the Subject Console in WISER (see Screen Shot 3):

1. Event Date
2. Reported Date
3. Reported by
4. If Grade 5, enter Death Date
5. If Grade 5, enter Death occurred: within 30 days
6. Event Narrative: Brief description (include brief clinical history relevant to this event, including therapies believed related to event). Begin narrative with the STRC clinician who was notified and Date/Time notified. In addition, state attribution by STRC clinician as either "Unrelated", "Unlikely", "Possibly", "Probably", or "Definitely". Always include the following here:
 - i. STRC clinician name and comments
 - ii. Date of last dose before the event
 - iii. Is suspension of the protocol needed? Y/N
7. Treating Physician comments
8. PI comments, if available
9. Protocol Attribution after discussion with STRC clinician

10. Outcome (Fatal/Died, Intervention for AE Continues, Migrated AE, Not Recovered/Not Resolved, Recovered/Resolved with Sequelae, Recovered/Resolved without Sequelae, Recovering and Resolving)
11. Consent form Change Required? Y/N
12. SAE Classification *This is required in order for the email notification to be sent*
13. Adverse Event Details – Enter all details for each AE associated with the SAE.
 - a. Course start date
 - b. Category
 - c. AE Detail
 - d. Comments
 - e. Grade/Severity
 - f. Unexpected Y/N
 - g. DLT Y/N
 - h. Attributions
 - i. Action
 - j. Therapy
 - k. Click ADD to attach the AE Detail to the SAE.
14. Enter Date Notified STRC -- *This is required for the email notification to be sent*
15. Click Submit. The auto-generated notification email will disseminate within 5 minutes.
If you do not receive an email within 5 minutes, check that you have entered the "Date Notified STRC" and the "SAE Classification". If these have been entered and the email still has not been received, take a screen shot of the SAE in WISER and immediately email it out to all of the STRC members listed in this SOP. In the subject line, indicate that this is a manual transmission of the SAE in lieu of the auto-generated email. It is required that a notification goes to the STRC members immediately so that their assessment can be obtained within the 24 hour time frame requirement. Contact the Cancer Center Programmer/Analyst to alert that there is an issue with the auto-generated email.

The Clinical Members of STRC to Notify by Phone or Page:

[name] – Director-at-Large, WFBCCC; Section Head, Hematology/Oncology

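### A non-fatal grade 4 wound infection during the index stay may be coded expected, because infection is the listed adverse event, and then escape mandatory STRC reporting

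*Combined protocol and SAP*

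**What the plan says.** Appendix C sets the STRC triggers. During protocol intervention and for 30 days afterwards, the reportable events are those "coded as either 1) unexpected grade 4, 2) unplanned inpatient hospitalization > 24 hours (regardless of grade), or grade 5 (death". Section 10.3 gives a shorter list: "STRC currently requires that all unexpected 4 and all grade 5 SAEs on these trials be reported to them for review". It does not mention hospitalization.

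On expectedness, Appendix C says: "Any grade 4 event that was not specifically listed as an expected adverse event in the protocol should be considered as unexpected". It then adds two further routes. A grade 4 event can be unexpected judged against the treatment "received or if it is unexpected based on the health of the patient". And "if there is any uncertainty about whether a grade 4 adverse event is expected or unexpected it should be reported to STRC".

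The adverse event list for tertiary closure (10.1) has one numbered entry, "10.1.1 Infection". Its text runs from skin redness through deep infection to the most serious form: "Rarely, a serious wound infection causes you to develop a fever or generalized infection". It also mentions readmission, intravenous antibiotics and further surgery. It gives no CTCAE grade. Section 10.2 refers the reader to a Section 7.1 for expectedness, but Section 7.0 is Data Management and has no subsections.

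On other oversight, Section 9.0 states: "The principal investigator will be responsible for the overall monitoring of the data and safety of study participants". Section 6.2 has one safety look, after five patients, and suspends the protocol only if all five have a wound or systemic infection. Section 10.4 sets out IRB reporting.

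**The concern.** Infection is the harm this closure technique is most obviously watched for, and it is also the event that the expectedness filter may remove from committee review. Section 10.1.1 presents wound infection as a risk of enrolment and describes enrolled patients as at medium to high risk of wound complications. Staff could reasonably read that as making infection expected.

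The result can be out of order. Under Appendix C, a lower-grade infection that leads to an unplanned readmission of more than 24 hours must be reported. A life-threatening one in a patient not yet discharged may not be. The index stay covers at least part of the period when the wound is open, and may include the bedside approximation planned for Day 4–7 (4.3.3).

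The STRC contact matters because it is the step at which staff must record whether the protocol should be suspended (Appendix C, notification step 4). A case that is not reported does not prompt that question.

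**Working it through.** The plan states no figure on this point. The main check sets the reporting rule against one event: a non-fatal grade 4 wound infection before first discharge.

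**1. Triggers in Appendix C**
- *Death:* not met.
- *Unplanned hospitalization over 24 hours:* not clearly met. The patient is already admitted, and prolongation of a stay is not named.
- *Unexpected grade 4:* depends on coding. If staff treat the 10.1.1 entry as a listing, the default sentence does not make the event unexpected. It is reportable if someone judges it unexpected for the treatment or for that patient, or is unsure.

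Section 10.3 adds no trigger to these. Adding the missing hospitalization trigger to 10.3 would not change the result for this event.

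**2. Other routes**
- *IRB (10.4):* adverse events are reported under institutional policy. The 7-calendar-day deadline is written for unanticipated problems, so a listed infection may fall outside it.
- *WISER (Appendix C):* all adverse events are entered, but STRC members are not notified until a notification date is filled in.
- *Interim rule (6.2):* it needs 5 of 5 infected. With independent patients and infection probability p, the chance is p^5. Using the infection rates in the Section 1.0 wound table:
  - contaminated, 20%: 0.20^5 = 0.0003
  - contaminated, 25%: 0.25^5 = 0.0010
  - dirty, 30%: 0.30^5 = 0.0024
  - dirty, 40%: 0.40^5 = 0.0102

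  The rule is therefore unlikely to bring a case to independent review, and it does not cover patients 6–20.

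**3. How often the situation might arise**

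Inputs: 20 patients (6.1) and a look after five (6.2), leaving 20 − 5 = 15. The documents give no rate q of grade 4 wound infection in the index stay, so 1–10% is an assumption. With independent patients and a common q, P(at least one) = 1 − (1 − q)^n.

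| Assumed q | Patients 6–20 (n = 15) | All 20 (n = 20) |
|---|---|---|
| 1% | 1 − 0.99^15 = 0.14 | 1 − 0.99^20 = 0.18 |
| 2% | 1 − 0.98^15 = 0.26 | 1 − 0.98^20 = 0.33 |
| 5% | 1 − 0.95^15 = 0.54 | 1 − 0.95^20 = 0.64 |
| 10% | 1 − 0.90^15 = 0.79 | 1 − 0.90^20 = 0.88 |

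These are chances that such an infection occurs, not that it goes unreported. Fatal cases, and cases judged unexpected or uncertain, would still reach the committee.

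**The case against.** A reader might infer that this infection meets no STRC trigger even with Appendix C applied in full, so that it reaches the committee only if fatal. The documents do not support that. Appendix C's remaining clauses can make a listed grade 4 event reportable, and doubt about expectedness is plausible here: 10.1.1 states no grade, does not call infection expected, describes generalized infection as rare, and the Section 7.1 pointer leads nowhere.

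Three further objections carry weight.
- The IRB and WISER routes mean the event is not outside all oversight.
- The upper assumed rates look high. The wound table gives 5–6% for infection of any grade in clean-contaminated wounds, the introduction says about two-thirds of gynecologic surgical site infections are superficial, and the six-patient series had none at sixty days. That series also had a median stay of 4 days, so much of the 30-day window falls after discharge, when a readmission over 24 hours is reportable under Appendix C.
- Appendix C is an institution-wide procedure that filters on expectedness by design, so a trial-specific addition is an improvement and not the correction of an error.

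What remains is that the safeguard depends on someone doubting the coding. The treatment and health clauses are weak for this event, because 10.1.1 names infection as a risk of enrolment in patients already at raised risk. Part of the doubt comes from the broken cross-reference. Correcting that alone would reduce the doubt and make an expected coding more likely.

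**Conclusion.** The concern holds in a limited form. A non-fatal grade 4 wound infection in the index stay may be coded expected and then need not go to the STRC. Only judgement-based clauses would catch it, and neither the IRB route, WISER entry nor the all-five interim rule starts STRC review in their place. It does not follow that such a case is certain to be missed.

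This conclusion rests on the wording of 10.1.1, 10.2, 10.3 and Appendix C, not on a rate. The 14–79% (patients 6–20) and 18–88% (all 20) figures rest on an assumed 1–10% rate and independent patients. The lower part of that range fits the documents' other figures better for clean-contaminated wounds; the table's rates for contaminated and dirty wounds are higher (20–40%), but also cover infections of any grade. The change is worth making because it is cheap and concerns patient safety.

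**What to change.** - **10.2:** correct the Section 7.1 pointer to Section 10.1, and state that listing infection there does not exempt a grade 4 infection from STRC reporting. Make both changes together.
- **10.3:** state that any grade 4 wound infection or wound-related systemic infection, including one during the index hospitalization, is reported to the STRC through the existing SAE console regardless of expectedness.
- **10.3 and Appendix C:** reconcile the two trigger lists, since 10.3 omits the hospitalization trigger.

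This changes reporting only; it leaves clinical management as written. The cost is a few sentences in Section 10 and perhaps a few extra console entries by existing staff across 20 patients. No new committee is needed.
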